9.3.3 Removal of Subjects From Therapy or Assessment

The investigator may withdraw the subject from the study at any time for safety or administrative reasons. The subject may stop study drug or withdraw from the study at any time for any reason.

9.4 Treatments

9.4.1 Treatments Administered

Subjects will be administered a single tablet of Belviq XR 20 mg or placebo orally QD at approximately the same time each day.

Belviq XR (lorcaserin hydrochloride) is a Drug Enforcement Administration (DEA) Scheduled IV Drug Product (C-IV) approved by the FDA.

Belviq XR will be provided as orange-colored, round, film-coated, biconvex 20-mg tablets (microcrystalline cellulose; mannitol, hypromellose 2208, ethylcellulose dispersion Type B, hypromellose 2910; colloidal silicon dioxide, polyvinyl alcohol, polyethylene glycol, titanium dioxide, talc, FD&C yellow #6/sunset yellow FCF aluminum lake, iron oxide yellow, iron oxide red, and magnesium stearate). Belviq XR and matching placebo will be supplied by the sponsor in labeled containers.

9.4.2 Identity of Investigational Product

9.4.2.1 Chemical Name, Structural Formula of Belviq XR

- Test drug code: APD356
- Generic name: lorcaserin hydrochloride
- Chemical name: (R)-8-chloro-1-methyl-2,3,4,5-tetrahydro-1H-3-benzazepine hydrochloride hemihydrate
- Molecular formula: $C_{11}H_{15}Cl_2N \cdot 0.5 H_2O$
- Molecular weight: 246.16 g/mol (hemihydrate form)

9.4.2.2 Comparator Drug

Not applicable

9.4.2.3 Labeling for Study Drug

Study drug will be labeled with text that is in full regulatory compliance with each participating country and is translated into the required language(s) for each of those countries.

The clinical study labels will contain, but are not limited to the following requirements:

1. Name and address of the sponsor
2. Pharmaceutical dosage form, quantity of dosage units, and strength
3. Lot number or Packaging Reference number
4. Protocol number
5. Directions of use (if applicable)
6. Storage conditions
7. Storage restrictions (if applicable)
8. US Caution Statement: “CAUTION: New Drug – Limited by Federal (US) law to investigational use.”

All packaging and labeling will be performed according to Good Manufacturing Practices and GCP guidelines.

Study drug must be stored as instructed on the study drug label and in accordance with the DEA Regulations for Schedule IV Controlled Drugs (US sites). Study drug must be kept in a secure location as required by DEA regulations and carefully stored at the study site within its original container.

The investigator (or pharmacist, as appropriate) must maintain records of the delivery of the study drug to the study site, the inventory at the site, use for each subject, and return of the study drug to a delegate of the sponsor. Total study site accountability will be conducted at the end of the study and the investigator must explain any discrepancies.

A Drug Dispensing Log must be kept current and should contain at least the following information:

- Identification (subject ID number and initials) of the subject to whom the study drug was dispensed
- The dates and unique kit or carton identifiers for dispensed study drug
- Initial inventory on receipt of drug at the site
- Final inventory on completion of the study

All records and inventory must be available for inspection by the clinical study monitor.

9.4.2.4 Storage Conditions

Where applicable, investigational product will be stored in accordance with the DEA Regulations for Scheduled III to V Drugs and labeled storage conditions. Temperature monitoring is required at the storage location to ensure that the study drug is maintained within an established temperature range. The investigator or designee is responsible for ensuring that the temperature is monitored throughout the total duration of the study and that records are maintained; the temperature should be monitored continuously by using either an in-house validated data acquisition system, a mechanical recording device, such as a

calibrated chart recorder, or by manual means, such that minimum and maximum thermometric values over a specific time period can be recorded and retrieved as required.

9.4.3 Method of Assigning Subjects to Treatment Groups

Subjects will be assigned to treatments based on a computer-generated randomization scheme that will be reviewed and approved by an independent statistician. The randomization scheme and identification for each subject will be included in the final clinical study report for this study.

Subjects will be centrally stratified by sex (male and female). Within each stratum, subjects will be randomized to receive either Belviq XR 20 mg or placebo QD in a 1:1 ratio.

Randomization will be performed centrally by an interactive voice or web response system (IxRS). The IxRS or clinical supply vendor will generate the randomized identification numbers to be included on study packaging. Upon signature of the ICF, the investigator or designee will access the IxRS to register the subject information. At Randomization, the IxRS will assign each subject a unique randomization number. At each subsequent visit during the Treatment Period and Follow-Up Period, the investigator or designee will access IxRS to obtain dispensing information and to register the subject's visit.

9.4.4 Selection and Timing of Dose for Each Subject

Subjects should take the study medication once daily at approximately the same time of every day, and be encouraged to take the study medication with an adequate amount of water (8 oz. or 240 mL).

9.4.5 Blinding

During the Randomization Phase, subjects and all personnel involved with the conduct and interpretation of the study, including investigators, site personnel, and sponsor staff will be blinded to the treatment codes. Randomization data will be kept strictly confidential, filed securely by an appropriate group with the sponsor or CRO, and accessible only to authorized persons (eg, Eisai Global Safety) until the time of unblinding, per the SOP.

A master list of all treatments and the subject numbers associated with them will be maintained in a sealed envelope by the clinical supply vendor, the IxRS vendor, and the sponsor. In the event that emergency conditions require knowledge of the study treatment given, the blind may be broken via the code breaker facility within the IxRS. Emergency procedures for revealing drug codes are given in [Section 9.5.4.5](#). If possible, before breaking the blind, the investigator should consult with the sponsor or designee to ascertain the necessity of breaking the code.

9.4.6 Prior and Concomitant Therapy

Any medication (including OTC medications) or therapy administered to the subject during the study (starting at the date of informed consent) will be recorded on the Prior and

Concomitant Medication Case Report Form (CRF) or Non-Pharmacological Procedures CRF. The investigator will record on the Adverse Event CRF any AE for which the concomitant medication/therapy was administered. If the concomitant medication/therapy is being administered for a medical condition present at the time of entry into the study, the investigator will record the medical condition on the Medical History and Current Medical Condition CRF.

Other products intended for weight loss including prescription drugs, OTC drugs, and herbal preparations are prohibited as concomitant medications. OTC cold medicines containing dextromethorphan can be used for up to 7 days and study medication is temporarily stopped for that time period and resumed the next day after the OTC cold medicine is stopped. Any of the following serotonergic agents in combination with Belviq XR is prohibited:

a. Serotonergic drugs

- SSRIs
- SNRIs
- TCAs
- bupropion
- triptans
- St. John's Wort
- tryptophan
- MAOIs
- linezolid
- dextromethorphan
- lithium
- tramadol
- antipsychotics or other dopamine antagonists

b. Others

- antiseizure medications including valproic acid, zonisamide, and lamotrigine
- oral steroids (topical or inhaled steroids are acceptable)
- stimulant medications (Ritalin, Concerta, Biphedamine and Dexedrine)
- benzodiazepines

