9 INVESTIGATIONAL PLAN

9.1 Overall Study Design and Plan

This is a multicenter, randomized, double-blind, placebo-controlled, parallel-group study in obese adolescents ages 12 to 17 years. Approximately 360 subjects will be randomized in a 1:1 ratio to Belviq XR 20 mg QD (180 subjects) and placebo (180 subjects). Subjects will be stratified by sex. Subjects will receive Belviq XR 20 mg or placebo QD in a 1:1 ratio for up to 52 weeks. Throughout the duration of the study, subjects will be encouraged to adhere to a lifestyle modification program that includes a standardized, age-appropriate diet and exercise counseling (see [Appendix 2](#)).

The study will consist of 2 phases: Prerandomization and Randomization. The Prerandomization Phase will last up to 30 days and consists of 1 visit during which subjects will be screened for eligibility. The Randomization Phase consists of a Treatment Period and a Follow-Up Period. The Treatment Period will last for a maximum of 52 weeks, with visits at Weeks 1, 5, 8, 12, 20, 28, 36, 44, and 52; the Follow-Up Period will extend from the End of Treatment (EOT) visit to the End of Study (EOS) visit.

Subjects who screen fail can be re-screened only once after 60 days. All subjects will continue in the study until the 52-week evaluation is completed. Subjects who discontinue treatment prematurely will be followed up until study completion.

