 7. Use of other products intended for weight loss including prescription drugs, over-the-counter (OTC) drugs, and herbal preparations within 1 month before Screening
 8. Use of any of the following medications:
 - a) Serotonergic drugs within 7 days (or 5 half-lives, whichever is longer) or monoamine oxidase inhibitors (MAOIs) within 30 days before Randomization, including:
 - selective serotonin reuptake inhibitors (SSRIs)
 - serotonin norepinephrine reuptake inhibitors (SNRIs)
 - tricyclic antidepressants (TCAs)

- bupropion
 - triptans
 - St. John's Wort
 - tryptophan
 - linezolid
 - dextromethorphan in any form (eg, OTC cold medicines)
 - lithium
 - tramadol
 - antipsychotics or other dopamine antagonists
- b) Others
- antiseizure medications including valproic acid, zonisamide, topiramate and lamotrigine
 - oral steroids (topical and inhaled steroids are acceptable)
 - stimulant medications (Ritalin, Concerta, Biphedamine and Dexedrine)
 - benzodiazepines
9. Use of drugs known to increase the risk for cardiac valvulopathy within 6 months before Screening, including but not limited to pergolide, ergotamine, methysergide, and cabergoline
 10. History or evidence of clinically significant disease (eg, malignancy; cardiac, respiratory, gastrointestinal, renal, or psychiatric disease) other than prediabetes (impaired fasting glucose or impaired glucose tolerance), Type 2 diabetes treated with oral anti-diabetic agents (excluding sulfonylurea) or non-insulin injectable antidiabetic agents, obstructive sleep apnea, dyslipidemia, and nonalcoholic fatty liver disease
 11. Use of Belviq XR within 6 months before Screening or hypersensitivity to Belviq XR or any of the excipients
 12. Significant change in diet or level of physical activity within 1 month before dosing or change in weight of more than 5 kg within 3 months before Screening
 13. Any use of a of very-low-calorie (<1000 calories/day) weight loss diet within 6 months before Screening
 14. History of alcohol or drug dependence or abuse
 15. Recreational drug use within 2 years before Screening
 16. Known to be human immunodeficiency virus positive
 17. Active viral hepatitis (B or C) as demonstrated by positive serology
 18. Malignancy within 5 years before Screening
 19. Unable to attend scheduled visits (eg, lack of transportation) or lack of a caregiver or guardian to supervise study participation

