9.5.1.5 Safety Assessments

Safety assessments will consist of monitoring and recording all AEs and serious adverse events (SAEs); electrocardiograms (ECGs); laboratory evaluations for hematology, metabolic function (glucose, lipids, and thyroid), adrenal functions, and biochemical blood and urine bone health assessments; blood chemistry and urine values; neuropsychiatric events; periodic measurements of vital signs, neuromuscular signs for screening potential serotonin syndrome, and signs and symptoms of priapism and prolactinemia; and performance of physical examinations. In subjects with potential prolactin-related AEs, such galactorrhea, changes in libido, or changes to menstrual cycle, prolactin level will be measured and assessed. Study drug effect on growth of adolescents will be evaluated using the CDC growth chart at Baseline, and Weeks 5, 12, 28, 36, 52, and at Follow-Up; a full physical examination at Baseline, Weeks 12, 28, 52, and at Follow-Up; and bone age determination by x-ray of the hand at Baseline, Weeks 12, 28, and 52. Sexual maturation will be evaluated by assessing sex hormones and self-reported changes in Tanner Staging at Baseline, Weeks 28 and 52, and at Follow-Up.

The C-SSRS will be used to assess all subjects in the study for any signal of depression or suicidal ideation or behavior. Additionally, screening, diagnosing, monitoring, and measuring the severity of depression will be assessed using the PHQ-9 and effects on cognitive function will be assessed using WRAML-2.

Echocardiographic assessments will be used to exclude subjects with FDA-defined valvulopathy, pulmonary hypertension, and other major cardiovascular disease (as outlined in Exclusion Criterion No. 3) during the Screening Period. Additionally, cardiac valvular function and pulmonary systolic pressure changes at Weeks 28 and 52 will be assessed. Valvular regurgitation as assessed in the echocardiogram will be rated absent, trace, mild, moderate, or severe for the aortic, mitral, and tricuspid valves; the rating will be absent or present for the pulmonic valve. The evaluations will be based on guidelines from the American Society of Echocardiography. Pulmonary artery pressure will be estimated from the tricuspid regurgitant jet velocity.

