Abnormal ECG (corrected QT interval [QTc]) results, if not otherwise considered part of a clinical symptom that is being reported as an AE, should be considered an AE if the QTc interval is greater than 450 msec and there is an increase of more than 60 msec from baseline. Any ECG abnormality that the investigator considers as an AE should be reported as such.

It is the responsibility of the investigator to review the results of the C-SSRS, PHQ-9, and WRAML-2 in all subjects and determine if any result constitutes an AE. Medical and scientific judgment should be exercised in deciding whether an isolated suicidality rating scale response should be classified as an AE (see [Section 9.5.1.5.9](#) for a description of the C-SSRS).

All AEs must be followed for 28 days after the subject's last dose or until resolution, whichever comes first. All SAEs must be followed to resolution or, if resolution is unlikely, to stabilization.

Every effort must be made by the investigator to categorize each AE according to its severity and its relationship to the study treatment.

Assessing Severity of Adverse Events

Adverse events will be graded on a 3-point scale (mild, moderate, severe) and reported in the detail indicated on the CRF. The definitions are as follows:

Mild Discomfort noticed, but no disruption of normal daily activity

Moderate Discomfort sufficient to reduce or affect normal daily activity

Severe Incapacitating, with inability to work or to perform normal daily activity

The criteria for assessing severity are different than those used for seriousness (see [Section 9.5.1.5.2](#) for the definition of an SAE).

Assessing Relationship to Study Treatment

Items to be considered when assessing the relationship of an AE to the study treatment are:

- Temporal relationship of the onset of the event to the initiation of the study treatment
- The course of the event, especially the effect of discontinuation of study treatment or reintroduction of study treatment, as applicable
- Whether the event is known to be associated with the study treatment or with other similar treatments
- The presence of risk factors in the study subject known to increase the occurrence of the event

- The presence of nonstudy, treatment-related factors that are known to be associated with the occurrence of the event

Classification of Causality

The relationship of each AE to the study drug will be recorded on the CRF in response to the following question:

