9.5.1.5.2 SERIOUS ADVERSE EVENTS AND EVENTS ASSOCIATED WITH SPECIAL SITUATIONS

An SAE is any untoward medical occurrence that at any dose:

- Results in death
- Is life-threatening (ie, the subject was at immediate risk of death from the AE as it occurred; this does not include an event that, had it occurred in a more severe form or was allowed to continue, might have caused death)
- Requires inpatient hospitalization or prolongation of existing hospitalization
- Results in persistent or significant disability/incapacity
- Is a congenital anomaly/birth defect (in the child of a subject who was exposed to the study drug)

Other important medical events that may not be immediately life-threatening or result in death or hospitalization but, when based on appropriate medical judgment, may jeopardize the subject or may require intervention to prevent one of the outcomes in the definition of SAE listed above should also be considered SAEs. Medical and scientific judgment should be exercised in deciding whether expedited reporting is appropriate in such situations.

For this study, the following events should always be considered serious and reported as an important medical event if it does not meet other serious criteria:

- Serotonin syndrome (must have at least 1 of the following: Spontaneous clonus; Inducible clonus plus agitation or diaphoresis; Ocular clonus plus agitation or diaphoresis; Tremor plus hyperreflexia; Hypertonia plus temperature above 38°C plus ocular clonus or inducible clonus)
- Psychosis
- Suicidal behavior

- Priapism
- New onset valvular heart disease
- New onset pulmonary hypertension
- Malignant neoplasms, with the exception of basal cell and squamous cell carcinomas of the skin
- Fibroadenomas of the breast or ductal carcinoma in situ

The following additional study specific AE of interest should be reported using the procedures detailed in Reporting of SAEs (Section 9.5.4.1), even if the study specific event does not meet serious criteria. If the event meets seriousness criteria, it should be reported as an SAE as above. However, if the event listed below does not meet serious criteria, it should be noted as nonserious on the Adverse Event CRF:

- Suicidal ideation
- Euphoria

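### Section 9.4.6 turns the other drug exclusions (criteria 7 and 8) into on-treatment bans but leaves out the valvulopathy-risk drugs of criterion 9, so a subject may start one between Screening and Week 52

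*Protocol*

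**What the plan says.** Section 9.3.2 has three consecutive exclusions for prior medication.

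- Criterion 7: "Use of other products intended for weight loss including prescription drugs, over-the-counter (OTC) drugs, and herbal preparations within 1 month before Screening".
- Criterion 8: serotonergic drugs and MAOIs, with washouts counted back from Randomization, plus antiseizure drugs, oral steroids, stimulants and benzodiazepines.
- Criterion 9: "Use of drugs known to increase the risk for cardiac valvulopathy within 6 months before Screening". It gives pergolide, ergotamine, methysergide and cabergoline as examples and is expressly not limited to them.

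Section 9.4.6 sets the rules after entry. On weight-loss products it says "Other products intended for weight loss including prescription drugs, OTC drugs, and herbal preparations are prohibited as concomitant medications". It then says "Any of the following serotonergic agents in combination with Belviq XR is prohibited" and gives list a (serotonergic drugs) and list b (others). Neither list mentions the criterion 9 drugs.

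On timing, Section 9.1 says "The Prerandomization Phase will last up to 30 days and consists of 1 visit"; treatment then lasts up to 52 weeks.

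On valve safety, the objectives name valvular function and pulmonary arterial pressure. Section 9.5.1.5 says "cardiac valvular function and pulmonary systolic pressure changes at Weeks 28 and 52 will be assessed". Section 9.5.1.5.2 puts "New onset valvular heart disease" among the events always treated as serious. Section 9.7.1.8 summarises the proportion of subjects developing FDA-defined valvulopathy by treatment group at Weeks 28 and 52.

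**The concern.** The protocol rejects a subject who took a valvulopathy-risk drug shortly before entry, yet it does not stop an enrolled subject from taking the same drug alongside study drug. The reason for the entry criterion, protecting the subject and keeping the valve findings interpretable, applies at least as strongly during exposure.

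The stake is safety and attribution. Safety data get no hypothesis test, so rare valve cases will be read descriptively and one by one. As an illustration, one case among the 180 subjects planned per arm is 1/180 = 0.56%. If that subject was also taking a drug known to raise valvulopathy risk, the case could not be assigned to study drug or cleared from it with any confidence. The BMI endpoints are not involved.

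**Working it through.** The protocol gives no figure to reproduce here. The check compares the entry criteria with the on-treatment list item by item and then counts the days left uncovered.

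**1. What is carried from Section 9.3.2 into Section 9.4.6**

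| Entry criterion | Items at entry | Items banned on treatment |
|---|---|---|
| 7, weight-loss products | 1 class | 1 class |
| 8a, serotonergic drugs | 12 bullets + MAOIs in the lead sentence = 13 | 13 |
| 8b, others | 4 classes | 4 classes |
| 9, valvulopathy-risk drugs | 4 named drugs, open class | 0 named drugs, no class entry |

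For criterion 8 this is 13 + 4 = 17 of 17; for criterion 9 it is 0 of 4. Two details on criterion 8:

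- The 17 of 17 is a count by class. Criterion 8b names topiramate and Section 9.4.6 does not, but the antiseizure class still covers it.
- Over-the-counter dextromethorphan is allowed for up to 7 days with study drug interrupted, so its ban carries a stated exception.

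**2. Whether another entry covers criterion 9**

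The nearest line in Section 9.4.6 is the one for antipsychotics and other dopamine antagonists. It neither names nor describes the criterion 9 drugs. The list is worded as closed, so a site cannot read further classes into it. No other section of the text reviewed prohibits these drugs after Screening.

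**3. Whether the eligibility recheck closes the screening gap**

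The schedule (Table 2) rechecks inclusion and exclusion criteria at Visit 2. Criterion 8a is anchored to Randomization, so the recheck covers drugs started during screening. Criterion 9 is anchored to Screening. Read literally, a drug started after Screening and before Day 1 does not breach it.

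**4. Length of the uncovered period**

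- Screening: up to 30 days (Section 9.1).
- Treatment: 52 × 7 = 364 days.
- Total: 30 + 364 = 394 days.
- With the +7-day window for the Week 52 visit: 394 + 7 = 401 days.

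This is the length of time without a ban. It does not measure how often such a drug would be used, which the protocol does not say.

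**The case against.** The best defence has four parts.

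- **No contradiction.** Criterion 9 and Section 9.4.6 do not conflict, and nothing requires every entry exclusion to be repeated as an on-treatment ban. The list is introduced as one of serotonergic agents. This is true, but list b already goes beyond serotonergic drugs and the weight-loss ban has nothing to do with serotonin. Section 9.4.6 is therefore the protocol's general list of prohibited medication.
- **Existing safeguards.** All medications are recorded from consent and reviewed at each visit from Screening to Week 52. Causality assessment must weigh "The presence of nonstudy, treatment-related factors that are known to be associated with the occurrence of the event". Section 9.5.7 has the investigator ask about care from other physicians and, with consent, inform them of the trial. The investigator may exclude an unsuitable subject (criterion 25) or withdraw one for safety (Section 9.3.3). These steps reduce the residual risk, and informing another physician could act before a prescription is written. None of them prohibits the drug. Criterion 7 and 8 drugs have the same safeguards, and the sponsor still banned those.
- **Small consequence.** Subjects are otherwise healthy adolescents, the trial is randomized and blinded, and safety is not tested. This stands: no bias between arms is expected unless use differs by arm, and the document gives no reason to think it would.
- **Incomplete text.** The file reviewed is the third of three parts, so this version's synopsis and any later amendment were not available. This also stands. Section 9.4.6 itself is complete in that part, and the earlier versions included there (the original, v2.0 and v3.0) have the same omission both in Section 9.4.6 and in the synopsis.

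**Conclusion.** The omission is real and worth correcting. Section 9.4.6 as printed carries over criterion 7 and all 17 classes of criterion 8, but none of the four criterion 9 drugs and no class statement for them. That leaves up to 394 days (401 with the visit window) in which a site following the text could allow a valvulopathy-risk drug.

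It matters more in this version than in v3.0. There, echocardiography was local and left to the investigator in subjects with signs or symptoms. Here it is scheduled for everyone and valve function is a named objective, yet the prohibited list was not aligned with that change.

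The conclusion covers Section 9.4.6 in the version reviewed. It claims no effect on the valvulopathy proportions, no bias between arms and no effect on the primary or key secondary analysis. It is a cheap improvement for subject safety and for the attribution of rare valve cases. Confidence is medium, because the frequency of use is unknown and not all of the protocol was available.

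**What to change.** Add one bullet to Section 9.4.6 prohibiting drugs known to raise the risk of cardiac valvulopathy. Reuse criterion 9's open wording and its four examples, and make the ban run from Screening through the Week 52 echocardiogram. Starting at Screening also closes the gap before Day 1 without rewording criterion 9. If the current synopsis repeats the prohibited list, make the same change there.

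The cost is one line of text. No new data are needed, because concomitant medications are already recorded. The downside is an occasional restricted choice of therapy or a recorded deviation.
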